589 hospitalizations, and tests.

590

591

592

593

594

595 **Annex 2 - Codelists**

596

597 **EXPOSURES: PPIs AND H2RAs**

598

- 599 ○ **IQVIA™ Disease Analyzer Germany**

600 *PPIs*

INN	EPHMRA ATC Code	EPHMRA ATC Text
ACETYLSALICYLIC ACID + ESOMEPRAZOLE	B01C5	Platelet aggregation inhibitors, combinations
AMOXICILLIN + OMEPRAZOLE + CLARITHROMYCIN	A02B2	Proton pump inhibitors
DICLOFENAC + OMEPRAZOLE	M01A1	Anti-rheumatics, non-steroidal plain
ESOMEPRAZOLE	A02B2	Proton pump inhibitors
LANSOPRAZOLE	A02B2	Proton pump inhibitors
NAPROXEN + ESOMEPRAZOLE	M01A1	Anti-rheumatics, non-steroidal plain
OMEPRAZOLE	A02B2	Proton pump inhibitors
PANTOPRAZOLE	A02B2	Proton pump inhibitors

601

602 *H2ARs*

INN	EPHMRA ATC Code	EPHMRA ATC Text
CIMETIDINE	A02B1	H2 antagonist
FAMOTIDINE	A02B1	H2 antagonist
NIZATIDINE	A02B1	H2 antagonist
RANITIDINE	A02B1	H2 antagonist

603

604

- 605 ○ **IQVIA™ Medical Research Data (IMRD) UK**

606 *PPIs*

Generic Drug Name
ESOMEPRAZOLE
LANSOPRAZOLE
OMEPRAZOLE
PANTOPRAZOLE
RABEPRAZOLE
KETOPROFEN/OMEPRAZOLE
NAPROXEN/ESOMEPRAZOLE
AMOXICILLIN/CLARITHROMYCIN/LANSOPRAZOLE
METRONIDAZOLE/CLARITHROMYCIN/LANSOPRAZOLE

607 H2ARs

Generic Drug Name
CIMETIDINE
FAMOTIDINE
NIZATIDINE
RANITIDINE
RANITIDINE BISMUTH CITRATE
CIMETIDINE/ALGINIC ACID
FAMOTIDINE/CALCIUM/MAGNESIUM

608

609

610 **OUTCOME: SEXUAL DYSFUNCTION**

611

612 ○ **IQVIA™ Disease Analyzer Germany**

613

WHO ICD10 code	WHO ICD10 Text
F52.0	Lack or loss of sexual desire
F52.1	Sexual aversion and lack of sexual enjoyment
F52.2	Failure of genital response
F52.3	Orgasmic dysfunction
F52.6	Nonorganic dyspareunia
F52.8	Other sexual dysfunction, not caused by organic disorder or disease
F52.9	Unspecified sexual dysfunction, not caused by organic disorder or disease
N48.4	Impotence of organic origin
N94.1	Dyspareunia
N48.3	Priapism -- Painful erection

614

615 ○ **IQVIA™ Medical Research Data (IMRD) UK**

Read code	Term
E2275	Inhibited male orgasm
67IA	Advice about impotence
7A6G0	Revascularisation for impotence
7A6G5	Ligation of penile veins for impotence
Eu521	Sexual aversion disorder
K27y1	Impotence of organic origin
1ABG	Sexual intercourse difficult
1ABB	Cannot get an erection
1ABC	Cannot sustain an erection
ZV417	Abnormal sexual function
15D	Pain on sexual intercourse
E2273	Impotence
E2273-1	Erectile dysfunction

Read code	Term
Eu520-3	[X] Lack of libido
Eu521-1	[X]Anhedonia sexual
7C25E	Management of erectile dysfunction
Eu522	Failure of genital response
Eu520-2	[X]Hypoactive sexual desire disorder
Eu523-1	[X]Inhibited orgasm
Eu520	Lack or loss of sexual desire
Eu522-2	[X]Male erectile disorder
Eu523	Orgasmic dysfunction
Eu52y	[X]Oth sex dysfunction, not caused by organic disorder/disease
Eu523-2	Anorgasmia
Eu522-3	Psychogenic impotence
Eu52	Non-organic sexual dysfunction
Eu52z	[X]Unspec sex dysfunction not caused by organic disorder/dis
K28y7	Dyspareunia due to non psychogenic cause in the male
E2272	Frigidity
E227-99	Frigidity and impotence
K580-99	Dyspareunia - non psychogenic
K27y1-99	Erectile dysfunction organic
EMISCDY1	Dyspareunia
EMISCPA6	Pain during or after sexual intercourse
EMISCIM4	Impotency
1D1B	C/O erectile dysfunction
EMISNQRE309	Reduced libido
EMISNQPR146	Problem getting an erection
EMISICD10 F5211	Lack of sexual enjoyment
K27y7	Erectile dysfunction due to diabetes mellitus
^ESCTLO263343	Low libido
^ESCTPS316073	Psychologic dyspareunia
^ESCTPA332307	Painful ejaculation
^ESCTOR351791	Orgasm incapacity
^ESCTPO357750	Poor erection
^ESCTDY366015	Dyspareunia
^ESCTOR384422	Orgasm disorder
^ESCTDO392066	Does not enjoy having sex
^ESCTIM451123	Impotence education
^ESCTDY479108	Dyspareunia due to non-psychogenic cause in the male
^ESCTDE494548	Decreased sexual function
^ESCTDR509827	Drug-induced impotence
^ESCTEN509828	Endocrine impotence
^ESCTCO509899	Coital failure
^ESCTSU524375	Superficial pain on intercourse
^ESCTDE524377	Deep pain on intercourse

Read code	Term
^ESCTDE524378	Deep dyspareunia
^ESCTSE524379	Sexual function painful
^ESCTDE526179	Delayed erection
^ESCTER526208	Erection without orgasm
^ESCTWE526211	Weak orgasm
^ESCTHY551800	Hypoactive sexual desire disorder
^ESCTPA562100	Pain on penetration
^ESCTDY572132	Dyspareunia - non-psychogenic
^ESCTER655321	Erectile dysfunction appliance
^ESCTSE748154	Secondary erectile dysfunction
^ESCTCO748662	Complaining of erectile dysfunction
^ESCT1395247	Erectile dysfunction
^ESCT1395249	Male erectile disorder
^ESCT1395253	Erectile dysfunction due to psychophysiologic disorder
^ESCT1409249	Erectile dysfunction due to diabetes mellitus
^ESCT1450429	Non-psychogenic dyspareunia

616

617

618 **FREQUENCY OF RECORDING OF SUBSTANCES AND CLINICAL CONDITIONS IN DATABASES**

619

620 Data on frequency of recording of the abovementioned substances and diagnosis in the databases are
621 provided upon request.

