	
Inclusion criteria:
 
 • Men aged 18 years or older; • With a recorded diagnosis for any of the following, prior to index date: GERD, gastric and duodenal ulcers, chronic gastroduodenitis, Zollinger-Elison syndrome, OR with a recorded recent history of comedication with any of the following: NSAIDs, acetyl salicylic and derivatives, glucocorticoids, or antithrombotic treatments; • With at least one year of recorded medical history prior index-date. 
Exclusion criteria:
 
 • Those with recorded prescription of any PPIs or H2RAs within one year before index-date; • Those with recorded history of SD OR treatment for SD at any time prior index-date; • Those with recorded history of selected severe central nervous system comorbidities (Section 4.3, Table 1) prior to index-date; • Those with history of Helicobacter pylori (H. pylori) infection or use of fixed PPI-antibiotic treatments for this indication.
Treatment protocols	
Initiate any of the following substances (or none of them in the “non-initiators” cohort) at index-date (see definition below), as monotherapy (i.e., not in combination with another PPI or H2RA).
 
Target arms:
 
 • esomeprazole (target arm [Cohort 1]) • omeprazole (target arm [Cohort 2]) 
Comparator arms:
 
 • pantoprazole (comparator arm [Cohort 3]) in the IQVIA™ Disease Analyser (DA) Germany database) • lansoprazole (comparator arm [Cohort 4]) in the IQVIA™ Medical Research Data (IMRD) UK database) • H2RAs, all combined (comparator arm [Cohort 5]) • non-initiators of either PPIs or H2RAs (comparator arm [Cohort 6])
Assignment procedures	
We will assume treatments are randomly assigned within levels of the covariates identified as potential confounders [see Section 4.6, Potential confounding factors]

Index-date (cohort entry, beginning of follow-up)	
Active treatment arms (including PPIs and H2RAs [Cohort 1 to 5]): The index date will be the date of the initiation of treatment defined as a prescription date for PPIs/H2RAs after a washout window of at least 365 days in which no previous prescription with any PPIs or H2RAs have been recorded.
 
Non-initiator arm [Cohort 6]: Non-initiator comparators will be selected on each date of the recruitment period when esomeprazole/omeprazole initiators start treatment,

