204 treatment episodes. Of note, eligibility criteria will be evaluated at each index-date every time the
205 patient contributes with a treatment episode. Figure 2 illustrates examples of patient exposure to
206 treatments for four different patients according to calendar time (in months).

[1] [Ranitidine-containing medicinal products - referral | European Medicines Agency \(europa.eu\)](https://www.ema.europa.eu/en/medicines/human/CTX/ranitidine)

207 **Figure 2.** Patient exposure to treatments according to calendar time.

208 Patient 1: Patient contributes with 1 treatment episode (first episode). The second episode does not meet the
 209 criterion of 1 year washout before index date.

210 Patient 2: Patient contributes with 1 treatment episode (first episode). The second episode does not meet the
 211 criterion of 1 year washout before index date.

212 Patient 3: Patient contributes with 2 treatment episodes. The second episode meets the criterion of 1 year washout
 213 before index date.

214 Patient 4: Patient contributes with 2 treatment episodes. The second episode meets the criterion of 1 year washout
 215 before index date.

216 The follow-up period illustrated here corresponds to the 12-month follow-up for the ITT analysis.

217 4.6. Variables

218 Exposure

219 a) Active treatment arm (cohorts):

220 Patients who **initiate treatment** with either target treatments (esomeprazole or omeprazole)
 221 or active comparators (pantoprazole, lansoprazole, H2RAs) during the study period will be
 222 identified based on the dates of prescriptions in the database and considering a washout period
 223 (See Figure 2 above) of 1 year before index-date in which no previous prescription with any
 224 PPIs or H2RAs have been recorded.

225 Only initiation of target treatments and active comparators as **monotherapy** will be included
 226 in the study. Initiating treatment with more than one PPI or H2RA or any combination of the
 227 two on the same day will be not allowed. However, combinations with treatments other than
 228 PPIs and H2RAs are allowed (e.g., alginates and antacid basic salts). Table 2 shows the
 229 treatment assignment by target/comparator arm.

230 Of note, considering that these treatments have been long available on the market, their
 231 prescribing pattern (on-demand or intermittent use) and widespread over-the-counter (OTC)
 232 use, it will not be possible to identify the first prescription ever (i.e., first use or incident

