 233 exposure) with any certainty. Electronic health records may not capture the entire patient
 234 history of utilisation of these treatments. In addition, these treatments are used
 235 interchangeably which would mean that a substantial number of individuals would be excluded
 236 from the study population if the study focuses only on first use ever of any of these
 237 substances. Therefore, the study will assess initiation of treatment after a washout window of
 238 at least 365 days.

239 Prescriptions will be identified through keyword searches using international non-proprietary
 240 names (INNs) in several prescription-related variables (e.g., "Therapy Name", "Product Name",
 241 "Molecule"). Detailed list of keywords used are provided in **Annex 2**.

242 PPIs will include the most prescribed substances in each database, i.e., esomeprazole,
 243 omeprazole, and pantoprazole in IQVIA™ DA Germany, and esomeprazole, omeprazole, and
 244 lansoprazole in IMRD UK. Other PPIs such as dexlansoprazole and rabeprazole are less
 245 commonly recorded in the selected databases and, therefore, will not be included in this study.

246 Products containing H2RAs will include the following substances (ordered by frequency of
 247 prescribing): ranitidine, famotidine, nizatidine, cimetidine in IMRD, and ranitidine, famotidine,
 248 cimetidine, nizatidine in IQVIA™ DA Germany.

249 **Annex 2** provides details on the use of PPI and H2RA substances over time in each database.

250

251 b) Non-initiators arm (cohort)

252 Non-initiator comparators will be randomly sampled and selected on each date of the
 253 recruitment period when esomeprazole/omeprazole initiators start treatment, **matched on**
 254 **birth-year**. This date will be the non-initiator comparators index-date. Thus, with regards to
 255 treatment, the active arms initiate a treatment on index-date and non-initiator comparators do
 256 not. Matching on index-date and on year of birth is meant to ensure a similar distribution of
 257 calendar time and age at index-date, both of which are considered important potential
 258 confounders.

259 It should be noted that *non-initiators* refer to patients who have selected indications (see Table
 260 1 above, inclusion criteria) recorded in the databases but who did not initiate therapy (i.e., did
 261 not have a recorded PPIs or H2RA prescription within 12 months before index-date or on index
 262 date).

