263 Table 2 summarises the treatment assignments by cohorts.

264

265 **Table 2.** Treatment assignment by cohorts.

Target treatments:	Active comparators:	Non-initiator comparator:

 • Treatment initiation as monotherapy* with: 
 ○ Esomeprazole [Cohort 1] 	
 • Treatment initiation as monotherapy* with: 
 ○ Selected PPIs: 	
 • Prior diagnosis of indication but no treatment

Target treatments:	Active comparators:	Non-initiator comparator:

 ○ Omeprazole [Cohort 2] 	
 ▪ Omeprazole [Cohort 2], when esomeprazole is the target treatment; ▪ Esomeprazole [Cohort 1], when omeprazole is the target treatment; ▪ Pantoprazole in IQVIA™ DA Germany [Cohort 3], or ▪ Lansoprazole in IMRD UK [Cohort 4] ○ Selected H2RAs [Cohort 5]: ranitidine, famotidine, cimetidine, nizatidine in IQVIA™ DA Germany, and ranitidine, famotidine, nizatidine, cimetidine in IMRD UK. 	
initiation with either PPIs nor H2RAs within previous 12-month or on index date [Cohort 6].

266 * **Note:** Treatment initiation with any combination with other PPIs or H2RAs on the index-date is not part of the
267 study.

268
269 **Outcome**

270 Sexual dysfunction (SD) will be defined as the first recorded occurrence of any of the following
271 conditions (ICD-10 code): lack or loss of sexual desire (F52.0); sexual aversion and lack of sexual
272 enjoyment (F52.1); failure of genital response (F52.2); orgasmic dysfunction (F52.3); nonorganic
273 dyspareunia (F52.6); other sexual dysfunction, not caused by organic disorder or disease (F52.8);
274 unspecified sexual dysfunction, not caused by organic disorder or disease (F52.9); impotence of
275 organic origin (N48.4); dyspareunia (N94.1), priapism, painful erection (N48.3).

276 **Annex 2** provides the list of WHO ICD-10 codes used to identify outcome events in IQVIA™ DA
277 Germany. READ codes were used to identify these conditions in IMRD UK (Annex 2). Of note, SD as
278 defined here is mostly driven by erectile dysfunction/impotence, which is the most frequent condition
279 recorded in both databases.

280
281 **Potential confounding factors:**

282 Analyses will account for the following baseline covariates measure before index-date, which are

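### Fixed NSAID/aspirin packs with esomeprazole or omeprazole can define the index treatment, and neither the arm rules nor the weights deal with the co-exposure they bring

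*Protocol*

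**What the plan says.** Annex 2, under its exposure heading, lists PPI-containing products for each database.

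- DA Germany: "ACETYLSALICYLIC ACID + ESOMEPRAZOLE", "NAPROXEN + ESOMEPRAZOLE" and "DICLOFENAC + OMEPRAZOLE".
- IMRD UK: "KETOPROFEN/OMEPRAZOLE" and a naproxen/esomeprazole product.

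Section 4.6 (Exposure) finds prescriptions by searching on substance names and points to this annex: "Detailed list of keywords used are provided in" Annex 2.

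Three rules bear on whether such a pack may start follow-up:

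- Box 2 requires initiation "as monotherapy (i.e., not in combination with another PPI or H2RA".
- Section 4.6 adds that combinations with treatments other than "PPIs and H2RAs are allowed (e.g., alginates and antacid basic salts". NSAIDs and aspirin are neither named nor barred.
- The only fixed combinations excluded are PPI-antibiotic packs, in the H. pylori criterion of Box 2.

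For adjustment, Section 4.6 introduces its confounder list with the words "Analyses will account for the following baseline covariates measure before index-date, which are" regarded as risk factors for the outcome. Neither NSAIDs nor aspirin is on that list. Section 4.7.3 then runs every analysis in the weighted population with no further adjustment.

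**The concern.** A man whose first qualifying prescription is an aspirin/esomeprazole pack starts two drugs on the same day. Followed literally, the protocol counts him as an esomeprazole initiator. Annex 2 offers no equivalent pack for pantoprazole, lansoprazole or any H2RA, so this form of co-initiation is tied to the target drugs. If the second drug, or the reason for giving it, carries a risk of sexual dysfunction, that risk is credited to esomeprazole or omeprazole.

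The protocol itself supplies a plausible path. The aspirin pack is coded as a platelet aggregation inhibitor. Section 4.6 counts atherosclerosis, myocardial infarction and stroke among the organic causes of sexual dysfunction. Section 4.9 concedes that histories in DA Germany may be fragmented and that comorbidity and comedication may be incompletely captured. An aspirin pack can therefore mark vascular risk that the recorded covariates miss.

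There is also a plain question of reproducibility. Annex 2 does not say which rows assign men to arms, so two programmers could build different versions of Cohorts 1 and 2.

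**Working it through.** The protocol gives no sample size, event rate or product share, so there is no figure to reproduce. The check has two parts.

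**1. Which products and which arms**

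Rows in Annex 2 with an NSAID or aspirin component:

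| Substance | DA Germany | IMRD UK | Total |
|---|---|---|---|
| Esomeprazole | 2 | 1 | 3 |
| Omeprazole | 1 | 1 | 2 |
| Pantoprazole | 0 | 0 | 0 |
| Lansoprazole | 0 | 0 | 0 |
| Any H2RA | 0 | 0 | 0 |

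The H2RA combinations listed are with alginate, antacid or bismuth only. The asymmetry is therefore complete against pantoprazole, lansoprazole, H2RAs and non-initiators. Table 2 also makes omeprazole a comparator for esomeprazole and the reverse. In that contrast both sides have such packs, and the imbalance is partial. These are counts of list rows, not of prescriptions.

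**2. Whether eligibility or weighting removes it**

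Recent NSAID or aspirin use is one of several alternative ways into the study (Box 2, Table 1). A man who qualifies through a GERD or ulcer diagnosis needs no earlier NSAID or aspirin, so his first one may be in the index pack. Covariates stop before the index date and do not see it. Earlier use is recorded for eligibility but is not in the weighting set.

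**3. Possible size**

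Assumed inputs, none of them in the protocol:

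- f: excess share of the target arm exposed to NSAID/aspirin because of the packs, 1% to 10%
- r: rate ratio for sexual dysfunction in exposed men, 1.2 to 1.5
- p0: share of the comparator exposed to NSAID/aspirin, 0 or 30%

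Spurious ratio = [1 + (p0 + f)(r − 1)] / [1 + p0(r − 1)]

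With p0 = 0 this reduces to 1 + f(r − 1):

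- f = 0.01, r = 1.2: 1 + 0.01 × 0.2 = 1.002
- f = 0.05, r = 1.5: 1 + 0.05 × 0.5 = 1.025
- f = 0.10, r = 1.5: 1 + 0.10 × 0.5 = 1.05

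With p0 = 0.30:

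- f = 0.10, r = 1.5: 1.20 / 1.15 = 1.043

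A harsher assumption, r = 2.0 with f = 0.10, gives 1.10 at p0 = 0 and 1.40 / 1.30 = 1.077 at p0 = 0.30. If r = 1 the ratio is exactly 1 whatever the share. For esomeprazole against omeprazole the factor cancels to 1 if the pack shares are equal.

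**The case against.** The strongest reply is that Annex 2 is not purely an index-treatment list. It contains rabeprazole and pantoprazole for IMRD and lansoprazole for DA Germany, which Section 4.6 does not make index treatments in those databases, and the antibiotic packs that Box 2 excludes. The list evidently also serves the washout and the switch-censoring of Section 4.7.4, and the NSAID/aspirin rows may be there for those purposes only. It is fair to say that counting them as index exposure is an inference. But the other surplus rows are ruled out by explicit text, and these five are not. Their role is left open by the protocol's own code list, which goes beyond detail normally left to a SAP.

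Four stronger readings are tempting, and the documents do not support them.

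- *The co-exposure is confined to the target arms in every comparison.* It is not: the two target drugs are comparators for each other, and a separately prescribed NSAID or aspirin may start alongside any active drug. Only the pack is product-specific.
- *Baseline covariates cannot capture it at all.* Some pack users will have earlier NSAID or aspirin use on record, which could be added to the weights. Recorded myocardial infarction, stroke and atherosclerosis are already in the set. What is missed is use that first starts in the pack.
- *Keeping these packs contradicts the exclusion of PPI-antibiotic packs.* That exclusion concerns the H. pylori indication, not fixed combinations as such. Table 1, footnote 2, accepts NSAID and antithrombotic comedication as an indication proxy.
- *The effect is largest because the esomeprazole arm is smaller.* The protocol gives no arm sizes.

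It also stands that the protocol nowhere names NSAIDs or aspirin as risk factors for sexual dysfunction. Even the direction of an effect is an assumption.

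**Conclusion.** The point holds as a gap in the exposure definition with a potential, probably small, bias. Five NSAID/aspirin packs can define the index treatment, they exist only for esomeprazole and omeprazole, and the adjustment as specified does not cover the drug that starts with them. The factor is about 1.002 to 1.05 if packs make up 1-10% of a target arm and carry 1.2-1.5 times the outcome rate. It is slightly less if NSAID/aspirin use is common in the comparator, and zero if there is no excess rate. Neither the share nor the rate ratio is in the documents, so this is not a demonstration that the hazard ratios will be biased. The case for acting is that the correction is cheap and the study is meant to inform a safety question in which a modest association could matter.

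**What to change.** 1. Mark each Annex 2 row as index-defining or as washout/censoring-only.
2. State in Section 4.6 that arms are assigned by single-ingredient PPI or H2RA products, antacid and alginate combinations apart. Keep the NSAID/aspirin packs for the washout, for non-initiator status and for censoring at a switch.
3. Add NSAID/aspirin use up to and including the index date to the weighting model. Without this, step 2 could reverse the imbalance: it would drop men who start both drugs in one esomeprazole or omeprazole pack but keep men who start pantoprazole, lansoprazole or an H2RA with a separate NSAID or aspirin. With it, separately prescribed co-initiation is balanced across the active arms.
4. Report a sensitivity analysis with the packs counted as index treatment.

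The cost is a flag on a few code-list rows, one extra set of covariates and one extra analysis. Some target-arm patients are lost: a man whose first prescription is a pack does not enter on that date, and the pack then counts against him in the one-year washout. The number should be small but cannot be estimated from the protocol.

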B. Non-treated comparators (non-initiators of either PPIs or H2RAs treatments)

- If the indication for treatment is a risk factor for the study outcome, then treated patients are more likely than non-treated to have the indication, and therefore are at a higher risk for adverse health outcomes associated with the indication, leading to confounding by indication. In this respect, the non-treated/non-user comparator is not the preferable comparator for safety studies.
- However, to our knowledge, the main treatment indications for PPIs (e.g., GERD, duodenal and gastric ulcers) have not been associated with SD. Thus, in this study, it is not expected that the estimate of the effect will be strongly biased by confounding by indication, which makes the comparison with non-treated patients acceptable. Additionally, the comparison with a non-treated group might provide insights into the background risk for SD, which will not be gained with the comparison with the selected active comparators in view of their potential risk for erectile dysfunction as mentioned above.
- The non-initiator group in this study might be a mixed group of non-users and [PPIs, H2RAs, alginates] OTC users for which a prescribing for either PPIs or H2RAs treatment is not required probably because of the presence of milder gastroduodenal conditions potentially requiring short term, occasional treatment in low doses.

Conclusion: In view of the above-mentioned advantages and disadvantages, we choose to use multiple comparators which could aid interpretation of the findings.

111

112

113 **4. Methods**

114

Box 2. Summary of study methods	
Recruitment period	01/01/2005 - 31/12/2020
Data sources	IQVIA™ Disease Analyser (DA) Germany IQVIA™ Medical Research Data (IMRD) UK
Eligibility criteria	
 ● Eligibility criteria will be applied at cohort entry (index-date, see definition below)

Box 2. Summary of study methods

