174 ¹ These indications are selected indications for PPIs and H2RAs. We restricted the study population to patients with
175 chronic indications, for which treatment is likely chronic. The rationale for this is explained in Limitations (first
176 paragraph)

177 ² These are assumed to be proxies of indications (e.g., PPIs are indicated to patients requiring continued NSAID or
178 antithrombotic therapy).

179

180 **4.4. Recruitment period**

181 The recruitment period will start on January 1st, 2005, and will end on December 31st 2020 in both
182 IQVIA™ DA Germany and IMRD UK.

183 Although the first use of esomeprazole dates to September 2000, in IMRD UK and October 2000, in
184 IQVIA™ DA Germany, we opted to include data from 2005 the year when the distribution of male
185 sexual dysfunction events started being consistent.

186 Additionally, we opted to limit the recruitment period up to 2020 because the use of H2RAs is very
187 limited in IQVIA™ DA Germany after 2020. Of note, the suspension of all ranitidine medicines in the
188 European Union due to the presence of low levels of an impurity called N-nitrosodimethylamine
189 (NDMA) in April, 2020^[1] led to the suspension of ranitidine, the dominant H2RA in Europe.

[figure not shown]
190

191 **4.5. Follow-up period**

192 Patients will be followed-up from index-date up to maximum one year. For instance, patients recruited
193 in 2020 can be followed up to 2021. Thus, patients will be followed-up from index-date to the earliest
194 of: date of first occurrence of outcome, loss to follow-up (e.g., transfer out date from the general
195 practice in IMRD or end of continuous observation of the patient by the practice in IQVIA™ DA
196 Germany, or date of last data collection from the practice), death (only available in IMRD UK), end of
197 follow-up (1 year) or end of the study period.

198 Considering the recommended duration for these treatments (4-8 weeks for PPIs and 8-12 weeks for
199 H2RAs), a patient may participate with several treatment episodes - and consequently index-dates -
200 during the study period. For example, a patient may receive a prescription for 8 weeks after which the
201 medication is discontinued to assess the need for ongoing therapy (on-demand or intermittent use).
202 After 15 months of discontinuing this therapy, the patient may receive another prescription for the
203 same therapy and duration. Therefore, this patient will enter the study twice and contribute with two

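### The H. pylori exclusion is in Box 2 but not in Table 1, and its fixed-pack limb, applied at the index date, reaches only omeprazole starters in Germany and lansoprazole starters in the UK

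*Protocol*

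**What the plan says.** Box 2 (section 4, exclusion criteria) removes "Those with history of Helicobacter pylori (H. pylori) infection or use of fixed PPI-antibiotic treatments for this indication". The criterion has two limbs joined by 'or' and states no look-back window for either. Box 2 also says: "Eligibility criteria will be applied at cohort entry (index-date, see definition below". Section 4.5 adds that eligibility is assessed again at each new index date.

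Table 1 (section 4.3), to which the text refers for the inclusion and exclusion criteria, lists three exclusions: recent PPI or H2RA prescription, prior sexual dysfunction or its treatment, and severe CNS disease. H. pylori is not among them.

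Annex 2 lists the exposure products. The German PPI list contains "AMOXICILLIN + OMEPRAZOLE + CLARITHROMYCIN". The UK PPI list contains "AMOXICILLIN/CLARITHROMYCIN/LANSOPRAZOLE" and "METRONIDAZOLE/CLARITHROMYCIN/LANSOPRAZOLE".

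Section 4.6 forbids starting two acid suppressants on the same day, but says that combinations with treatments other than "PPIs and H2RAs are allowed (e.g., alginates and antacid basic salts"). Footnote 1 to Table 1 describes the population as restricted to "chronic indications, for which treatment is likely chronic".

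**The concern.** An active-comparator design relies on one eligibility rule that selects the same kind of patient in each arm. Here one limb of a rule identifies an eradication course by how it is packaged, and the packs exist for one PPI per database. Two men given the same antibiotics with their index PPI can be treated differently according to which PPI they received and whether the course came as a pack.

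The affected contrasts are esomeprazole versus omeprazole and omeprazole versus pantoprazole or H2RAs in Germany, and esomeprazole or omeprazole versus lansoprazole in the UK. If men on a short eradication course differ in risk of sexual dysfunction from men treated for longer, the arms differ for a reason unrelated to the drug. The missing Table 1 entry adds a second uncertainty: a programmer working from Table 1 would keep pack users that Box 2 removes.

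**Working it through.** The protocol states no figure on this point, so the check sets its parts side by side. An illustration under assumed inputs follows.

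**1. Which products can trigger the fixed-pack limb (Annex 2, counted by hand)**

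| List | Entries | Entries with an antibiotic | Acid suppressant in them |
|---|---|---|---|
| Germany, PPIs | 8 | 1 | omeprazole |
| Germany, H2RAs | 4 | 0 | none |
| UK, PPIs | 9 | 2 | lansoprazole (both) |
| UK, H2RAs | 7 | 0 | none |

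**2. A man with no recorded infection who starts an eradication course on the index date**

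- Germany, omeprazole: excluded if given as the pack, kept if given as separate items.
- Germany, esomeprazole, pantoprazole or H2RA: no listed pack exists, so he is kept.
- UK, lansoprazole: excluded if given as a pack, kept if given as separate items.
- UK, esomeprazole, omeprazole or H2RA: no listed pack exists, so he is kept.

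The monotherapy rule in section 4.6 does not remove him, because antibiotics are neither PPIs nor H2RAs.

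**3. Whether weighting repairs this.** Confounder lists (i) to (v) in section 4.6 contain neither H. pylori nor antibiotics, so the treatment weights do not balance it.

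**4. Contrasts not touched by index-date packs.** Esomeprazole versus pantoprazole or H2RAs in Germany. Esomeprazole versus omeprazole, and either of them versus H2RAs, in the UK.

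**5. Illustrative size (all inputs assumed).** Let s be the share of index starts in an arm that are eradication courses without a recorded infection (2% to 10%). Let p be the share of those in the German omeprazole arm that are packs and so excluded (50% to 100%). Assume a true hazard ratio of 1.50 against non-initiators for sustained use of either drug, and no effect in short-course men. An arm with residual share r then reads 1 + 0.5(1 − r). For esomeprazole r = s. For omeprazole r = s(1 − p)/(1 − sp). The true esomeprazole versus omeprazole ratio is 1.00.

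Same s in both arms:

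- s = 2%, p = 50%: r = 0.010/0.990 = 0.0101, ratio 1.490/1.4949 = 0.997.
- s = 10%, p = 50%: r = 0.050/0.950 = 0.0526, ratio 1.450/1.4737 = 0.984.
- s = 10%, p = 100%: r = 0, ratio 1.450/1.500 = 0.967.

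Different s (esomeprazole 2%, omeprazole 10%):

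- No exclusion: 1.490/1.450 = 1.028.
- p = 50%: 1.490/1.4737 = 1.011.
- p = 100%: 1.490/1.500 = 0.993.

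With unequal shares the pack exclusion brings the ratio closer to 1, and the sign of what remains depends on p.

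**The case against.** The strongest reply is that the infection limb does most of the work and is the same for all arms. It carries no look-back limit and removes any man with recorded H. pylori, including one given separate items. That stands, and it confines the gap to courses with no recorded infection. Such courses are plausible: section 4.9 says medical history may be incomplete, particularly in the German database, where practices are not linked. Section 4.9 also says that misclassification will affect both target and comparator groups. That does not settle the point, because a pack reveals the regimen in one arm only.

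A reader might infer that packs can remove men from one arm only and never from the esomeprazole, pantoprazole or H2RA cohorts. The documents do not support this. Pack use has no time window, so an earlier pack would exclude a man from any arm, non-initiators included. Packs are also listed as PPIs, so use within the past year already fails the washout. The asymmetry concerns packs prescribed on the index date. Separate-item courses also stay in the omeprazole and lansoprazole arms.

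A reader might also infer a one-directional bias that flatters esomeprazole. That needs an equal share of eradication courses in both arms, which no document gives; the unequal case above shows the sign can change. The assumption of no short-course effect also sits poorly with the case reports in section 2, where onset ranged from a few days to five months. Any dilution against non-initiators comes from separate-item courses remaining in the arms, not from the pack rule.

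Finally, footnote 1 to Table 1 says treatment is likely chronic; it does not promise that short courses are absent. Section 4.5 itself gives a recommended duration of 4 to 8 weeks for PPIs.

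**Conclusion.** The point holds in a limited form. Box 2 and Table 1 disagree on whether there is an H. pylori exclusion, and that needs no assumption to establish. Within Box 2, the fixed-pack limb makes eligibility at the index date non-equivalent for the contrasts named above, among men without a recorded infection. This follows from the Annex 2 lists and the co-prescription rule.

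The size cannot be derived: the protocol gives no frequency of pack use, H. pylori recording or separate-item regimens. Under the assumed inputs, the shifts run from 0.967 to 1.011 around a true 1.00, and the low end needs every extreme at once. The bias is probably small and its direction is unknown. This is a cheap improvement to the definition and does not threaten the design.

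**What to change.** State one exclusion in identical words in Box 2 and Table 1, for all arms and both databases. Exclude an index episode with any of:

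- a recorded H. pylori infection up to and including the index date;
- a fixed PPI-antibiotic pack;
- a same-day prescription, with the index PPI or H2RA, of at least two of the antibiotics named in the Annex 2 packs (amoxicillin, clarithromycin, metronidazole).

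Apply the same history rule to non-initiators.

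The cost is one sentence in each place, plus an antibiotic keyword list in Annex 2 and its extraction; Annex 2 currently lists no antibiotics as separate products. A few men given two of these antibiotics for another reason will be lost. Reporting the number removed by each limb, by arm and database and subject to the low-cell rules in section 5, would show whether the issue mattered.
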